# 9.2.3. Plans for Disseminating and Communicating Study Results

GSK will provide the investigator with the full summary of the study results.

The procedures and timing for public disclosure of the protocol and results summary and for development of a manuscript for publication for this study will be in accordance with GSK Policy.

A manuscript will be progressed for publication in the scientific literature if the results provide important scientific or medical knowledge.

#### 9.2.4. Data Quality Assurance

- All participant data relating to the study will be recorded on printed or eCRF unless transmitted to the sponsor or designee electronically (e.g., laboratory data). The investigator is responsible for verifying that data entries are accurate and correct by physically or electronically signing the CRF.
- The investigator must maintain accurate documentation (source data) that supports the information entered in the CRF.
- The investigator must permit study-related monitoring, audits, IEC review, and regulatory agency inspections and provide direct access to source data documents.
- Monitoring details describing strategy (e.g., risk-based initiatives in operations and quality such as Risk Management and Mitigation Strategies and Analytical Risk Based Monitoring), methods, responsibilities and requirements, including handling of noncompliance issues and monitoring techniques (central, remote, or on site monitoring) are provided in the Monitoring Plan.
- The sponsor or designee is responsible for the data management of this study including quality checking of the data.
- The sponsor assumes accountability for actions delegated to other individuals (e.g., Contract Research Organisations [CROs]).
- Study monitors will perform ongoing source data verification to confirm that data entered into the CRF by authorised site personnel are accurate, complete, and verifiable from source documents; that the safety and rights of participants are being protected; and that the study is being conducted in accordance with the currently approved protocol and any other study agreements, Ethical Guidelines for Medical and Health Research Involving Human Subjects, and all applicable regulatory requirements.
- Records and documents, including signed ICF, pertaining to the conduct of this study must be retained by the investigator for 10 years from the issue of the final Clinical Study Report (CSR) or equivalent summary unless local regulations or institutional policies require a longer retention period. No records may be destroyed during the retention period without the written approval of the sponsor. No records may be transferred to another location or party without written notification to the sponsor.

#### 9.2.5. Source Documents

Source documents provide evidence for the existence of the participant and substantiate the integrity of the data collected. Source documents are filed at the investigator's site. The definition of what constitutes source data will be found in the source data agreement.

213684

Data reported on the CRF or entered in the eCRF that are transcribed from source documents must be consistent with the source documents or the discrepancies must be explained. The investigator may need to request previous medical records or transfer records, depending on the study. Also, current medical records must be available.

#### 9.2.6. Study and Site Closure

GSK or its designee reserves the right to close the study site or terminate the study at any time for any reason at the sole discretion of GSK. Study sites will be closed upon study completion. A study site is considered closed when all required documents and study supplies have been collected and a study-site closure visit has been performed.

The investigator may initiate study-site closure at any time, provided there is reasonable cause and sufficient notice is given in advance of the intended termination.

Reasons for the early closure of a study site by the sponsor or investigator may include but are not limited to:

- Failure of the investigator to comply with the protocol, the requirements of the IEC or local health authorities, the sponsor's procedures, or Ethical Guidelines for Medical and Health Research Involving Human Subjects;
- Inadequate recruitment of participants by the investigator.

#### 9.2.7. Publication Policy

The results of this study may be published or presented at scientific meetings. If this is foreseen, the investigator agrees to submit all manuscripts or abstracts to the sponsor before submission. This allows the sponsor to protect proprietary information and to provide comments.

The sponsor will comply with the requirements for publication of study results. In accordance with standard editorial and ethical practice, the sponsor will generally support publication of multi-center studies only in their entirety and not as individual site data. In this case, a coordinating investigator will be designated by mutual agreement.

Authorship will be determined by mutual agreement and in line with International Committee of Medical Journal Editors authorship requirements.

# 9.3. APPENDIX 3: ADVERSE EVENTS: DEFINITIONS AND PROCEDURES FOR RECORDING, EVALUATING, FOLLOW-UP, AND REPORTING

#### 9.3.1. Definition of an AE

#### **AE Definition**

 An AE is any untoward medical occurrence in a clinical study participant, temporally associated with study participation, whether or not considered related to study participation.

NOTE: An AE can therefore be any unfavourable and unintended sign (including an abnormal laboratory finding), symptom, or disease (new or exacerbated) temporally associated with study participation.

#### **Events Meeting the AE Definition**

- Any abnormal laboratory test results (haematology, clinical chemistry, or urinalysis) or other safety assessments (e.g., ECG, radiological scans, vital signs measurements), including those that worsen from baseline, considered clinically significant in the medical and scientific judgment of the investigator (i.e., not related to progression of underlying disease).
- Exacerbation of a chronic or intermittent pre-existing condition including either an increase in frequency and/or intensity of the condition.
- New conditions detected or diagnosed after study entry even though it may have been present before the start of the study.
- Signs, symptoms, or the clinical sequelae of a suspected drug-drug interaction.
- Signs, symptoms, or the clinical sequelae of a suspected overdose of a concomitant medication. Overdose per se will not be reported as an AE/SAE unless it is an intentional overdose taken with possible suicidal/self harming intent. Such overdoses should be reported regardless of sequelae.
- The signs, symptoms, and/or clinical sequelae resulting from lack of efficacy will be reported as AE or SAE if they fulfill the definition of an AE or SAE. Also, "lack of efficacy" or "failure of expected pharmacological action" constitutes an AE or SAE.

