#### **Events NOT Meeting the AE Definition**

- Any clinically significant abnormal laboratory findings or other abnormal safety assessments which are associated with the underlying disease, unless judged by the investigator to be more severe than expected for the participant's condition.
- The disease/disorder being studied or expected progression, signs, or symptoms of the disease/disorder being studied, unless more severe than expected for the participant's condition.
- Medical or surgical procedure (e.g., endoscopy, appendectomy): the condition that leads to the procedure is the AE.
- Situations in which an untoward medical occurrence did not occur (social and/or convenience admission to a hospital).

213684

• Anticipated day-to-day fluctuations of pre-existing disease(s) or condition(s) present or detected at the start of the study that do not worsen.

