#### 9.3.2. Definition of an SAE

If an event is not an AE per definition above, then it cannot be an SAE even if serious conditions are met (e.g., hospitalisation for signs/symptoms of the disease under study, death due to progression of disease).

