4.2. Primary Endpoint(s) Analyses

4.2.1. Definition of endpoint(s)

The primary endpoints are as follows:

- Frequency of adverse events (AEs) / serious adverse events (SAEs)
- Frequency of AEs related to Nucala (adverse drug reactions, ADRs)
- Frequency of AEs of special interests (AESI)

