4.2.2. Main analytical approach

The primary analyses will be based on the TP. Adverse events (AEs) will be coded using the Medical Dictionary for Regulatory Activities (MedDRA), with the maximum intensity of each AE determined by the investigator (as mild, moderate, severe or unknown).

All AEs, ADRs, SAEs, AEs leading to withdrawal from study, and AESIs will be summarized by the observation period and the total period (the observation period and the follow-up period), respectively. A separate summary of AEs by maximum intensity will be produced by the observation period and the total period, respectively.

The frequency and percentage of all AEs will be summarized and displayed in two ways: 1) in descending order by PT only and 2) in descending order by SOC and PT.

Separate summaries will be provided for ADRs. An ADR is defined as an AE for which the investigator classifies the possible relationship to study intervention as "Yes". A worst-case scenario approach will be taken to handle missing relatedness data, i.e. the summary table will include events with the relationship to study intervention as 'Yes' or missing. The summary table will be displayed by SOC and PT. The relationship of primary SOCs, Preferred Terms, and verbatim texts will be listed.

The number and percentage of participants who experienced the serious adverse event will be summarized.

The following will be considered adverse events of special interest (AESI) for the purpose of analyses: Hypersensitivity (including anaphylaxis), infections and malignant tumors, defined as safety specifications in the Japanese RMP.

AESI	Definition	Dictionary code
Hypersensitivity (including anaphylaxis)	Anaphylaxis reaction (SMQ/narrow)	20000021 (narrow)
	Excluding "10078117: Eosinophilic granulomatosis with polyangiitis" from PT contained in Hypersensitivity (SMQ/narrow)	20000214 (narrow)
Infections	Infections: Infections and infestations(MedDRA/J SOC)	MedDRA/J SOC: 10021881
Malignant tumors	Malignant tumors (SMQ/narrow)	20000227 (narrow) 20000228 (narrow)
	Lymphoma malignum (SMQ/narrow)	20000215 (narrow)

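### The AE definition both counts lack of efficacy as an AE or SAE and excludes the disease under study, so whether an EGPA flare enters the primary AE/SAE frequency depends on how the site reads it

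*Protocol*

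**What the plan says.** **What brings an event in.** In Protocol Section 9.3.1, the list of events meeting the AE definition has a bullet on lack of efficacy with two sentences. The first is conditional: clinical findings "resulting from lack of efficacy will be reported as AE or SAE if they fulfill the definition of an AE or SAE". The second carries no condition: lack of efficacy, or "failure of expected pharmacological action' constitutes an AE or SAE". A separate bullet in the same list admits "Exacerbation of a chronic or intermittent pre-existing condition including either an increase in frequency and/or intensity of the condition", with no exception for EGPA.

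**What keeps an event out.** The companion list of events not meeting the definition contains "The disease/disorder being studied or expected progression, signs, or symptoms of the disease/disorder being studied, unless more severe than expected" for that participant. What counts as more severe than expected is not defined. Section 9.3.2 adds: "If an event is not an AE per definition above, then it cannot be an SAE even if serious conditions are met". Its examples are "hospitalisation for signs/symptoms of the disease under study, death due to progression of disease".

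**What the SAP does with the result.** AE and SAE frequency is the primary endpoint (SAP 4.2.1). SAP 4.2.2 tabulates all AEs and SAEs as reported and also gives event rates per 1000 participant-years. The preferred term "Eosinophilic granulomatosis with polyangiitis" is taken out of the hypersensitivity AESI only. SAP 4.2.3 plans no sensitivity analysis.

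**The concern.** The two lists overlap on the event that is closest to the study question. A participant admitted with an EGPA flare while still receiving Nucala shows both a possible failure of drug action and a manifestation of the disease under study. The protocol does not say which rule takes precedence, so two sites following it in good faith can record the same admission differently.

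The study is single-arm and descriptive, with no hypothesis test (SAP Section 2). The reported frequency is itself the primary result, with no comparator in which a classification habit might cancel out. If the SAE percentage partly reflects site reading, it is hard to interpret or to set beside other Nucala data.

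Asthma has the same difficulty. Protocol Section 1 describes EGPA as characterised by asthma, which suggests the disease under study. Section 4.7 lists asthma as an example of a current medical condition, which suggests a pre-existing condition whose exacerbation is an AE.

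**Working it through.** **1. The plan's own figure.** Protocol Section 3.5 and SAP Section 5 size the study to see at least one case of an AE with frequency p = 1.5%. With n = ln(1 − P) / ln(1 − p):

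- P = 80%: ln(0.20) / ln(0.985) = 106.49, so 107 (stated 107)
- P = 70%: 79.66, so 80 (stated 80)
- P = 90%: 152.35, so 153 (stated 153)
- 10% dropout: 107 / 0.90 = 118.9, so 119 (stated as approximately 120)

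The figures reproduce. The AE definition does not enter the calculation, so the sample size is not touched.

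**2. One admission read through the text.** A participant on continued Nucala is hospitalised with an EGPA flare.

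| How the site reads it | Rule used | AE? | SAE? |
|---|---|---|---|
| The drug has failed | 9.3.1, second lack-of-efficacy sentence | Yes | Yes, hospitalised |
| A chronic pre-existing condition has worsened | 9.3.1, exacerbation bullet | Yes | Yes, hospitalised |
| Disease under study, more severe than expected | 9.3.1, exception to the exclusion | Yes | Yes, hospitalised |
| Disease under study, as expected | 9.3.1 exclusion, then 9.3.2 | No | No |

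All four readings rest on current text. The third and fourth differ only by an investigator judgement that has no criterion. The first two bypass that judgement.

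**3. Effect on the SAE proportion.** The documents give neither a flare rate nor a background SAE rate, so both are assumed. Let f be the proportion of participants with a hospitalised EGPA flare and b the proportion with another SAE, taken as independent. With all flares excluded the SAE proportion is b. With all counted it is 1 − (1 − b)(1 − f), a shift of f(1 − b).

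| b (assumed) | All excluded | f = 5% | f = 15% | f = 30% |
|---|---|---|---|---|
| 5% | 5% | 9.8% | 19.3% | 33.5% |
| 10% | 10% | 14.5% | 23.5% | 37.0% |
| 20% | 20% | 24.0% | 32.0% | 44.0% |

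For example, with b = 10% and f = 5%, 1 − 0.90 × 0.95 = 14.5%. With 120 participants, f = 5% to 30% is 6 to 36 people. The two ends, all out and all in, are bounds under these assumptions. Mixed site practice would fall between them.

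**4. Effect on the exposure-adjusted rate.** SAP 4.2.2 counts events, so repeated flares in one participant add up under one reading and disappear under the other. If all 120 participants had 96 weeks of exposure, the denominator is 120 × 96 × 7 / 365.25 = 220.8 participant-years. One event is then worth 1000 / 220.8 = 4.5 per 1000 participant-years. Six to 36 single admissions would move the SAE rate by about 27 to 163 per 1000.

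**5. Scale without a flare assumption.** Two participants whose admissions are classified differently move a preferred-term row by 2 / 120 = 1.7%. That is about the 1.5% frequency the study was sized to detect.

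**The case against.** The strongest reply is that the text, read as a whole, already has a default. A flare consists of signs and symptoms. The first lack-of-efficacy sentence sends those back to the AE definition and so to its exclusions. The disease-specific exclusion would ordinarily prevail over the general exacerbation bullet, and Section 9.3.2 names this very type of admission. The unconditional sentence would then cover only a separate report of lack of efficacy.

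This is a reasonable reading, but it does not close the gap. A separate lack-of-efficacy entry for the same admission would still put that admission into the SAE count under another term. The protocol also does not state that this reading governs.

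Other points on that side stand in part:

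- Relapse, EGPA hospitalisation and emergency or unscheduled visits are secondary endpoints (SAP 4.3.1), and asthma exacerbation is also analysed (Protocol Section 4.6). AEs are shown by preferred term and listed. Recorded flares are therefore visible, but those left out of the AE data do not appear in the AE tables.
- The protocol refers to an eCRF entry guideline, a study reference manual and pharmacovigilance training. These may contain an instruction, but they are not among the documents available here.
- A protocol amendment needs ethics committee approval (Protocol Section 6). SAP version 5.0 dates from May 2023, so a late change in reporting could leave early and late events recorded differently.

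**Conclusion.** The conflict is real and bears on the primary endpoint, but it is limited in scope. It concerns the AE and SAE frequencies and the exposure-adjusted rates, and it can be handled cheaply. Its size is unknown. The range of 14.5% to 37.0% against 10% rests entirely on assumed flare rates of 5% to 30%, an assumed independent 10% with other SAEs, and all flares switching class together.

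A reader might infer more than the documents support:

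- *That signs of EGPA can never be an AE.* The exclusion admits those more severe than expected, and Section 9.3.2 bars only events that fail the AE definition.
- *That the SAP expects flares in the AE data as a matter of routine, because it removes the EGPA term from the hypersensitivity AESI.* The removal is equally consistent with only the more severe flares being reported.
- *That flares are among the likeliest serious events here.* No rate is given, and Protocol Section 5 describes a cohort selected for good response to Nucala.
- *That flares are lost to the study, or that the SAE frequency is meaningless.* Flares are collected separately, and the frequency is ambiguous only for events that overlap with EGPA.

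**What to change.** 1. **Protocol Sections 9.3.1 and 9.3.2.** Reconcile the lack-of-efficacy bullet, the exacerbation bullet, the disease-under-study exclusion and the SAE examples, so that one stated rule governs EGPA flares and lack-of-efficacy reports. Say how EGPA-related asthma is handled. Which rule to adopt is for the sponsor.
2. **SAP 4.2.2, the main remedy.** Show overall AE and SAE frequencies and exposure-adjusted rates twice: as reported, and without a prespecified list of EGPA, asthma and lack-of-efficacy preferred terms. For events coded to those terms, the second version does not depend on site classification. A flare coded only as an organ-level symptom would remain, so the list needs care. The as-reported version should stay, because the restricted one also drops flares validly reported as more severe than expected.
3. **SAP 4.2.2, one listing.** List EGPA hospitalisations that were not recorded as SAEs. The schedule of activities (Protocol Section 9.1) already collects them.

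Items 2 and 3 cost a few table rows and one listing, with no new data. Item 1 costs an amendment. If made late, it may leave earlier events recorded under a different understanding, so it should not be relied on alone.

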#### **Events NOT Meeting the AE Definition**

- Any clinically significant abnormal laboratory findings or other abnormal safety assessments which are associated with the underlying disease, unless judged by the investigator to be more severe than expected for the participant's condition.
- The disease/disorder being studied or expected progression, signs, or symptoms of the disease/disorder being studied, unless more severe than expected for the participant's condition.
- Medical or surgical procedure (e.g., endoscopy, appendectomy): the condition that leads to the procedure is the AE.
- Situations in which an untoward medical occurrence did not occur (social and/or convenience admission to a hospital).

213684

• Anticipated day-to-day fluctuations of pre-existing disease(s) or condition(s) present or detected at the start of the study that do not worsen.

#### 9.3.2. Definition of an SAE

If an event is not an AE per definition above, then it cannot be an SAE even if serious conditions are met (e.g., hospitalisation for signs/symptoms of the disease under study, death due to progression of disease).

#### An SAE is defined as any untoward medical occurrence that, at any dose:

#### Results in death

#### Is life-threatening

The term 'life-threatening' in the definition of 'serious' refers to an event in which the participant was at risk of death at the time of the event. It does not refer to an event, which hypothetically might have caused death, if it were more severe.

#### Requires inpatient hospitalisation or prolongation of existing hospitalisation

In general, hospitalisation signifies that the participant has been detained (usually involving at least an overnight stay) at the hospital or emergency ward for observation and/or treatment that would not have been appropriate in the physician's office or outpatient setting. Complications that occur during hospitalisation are AEs. If a complication prolongs hospitalisation or fulfils any other serious criteria, the event is serious. When in doubt as to whether "hospitalisation" occurred or was necessary, the AE should be considered serious.

Hospitalisation for elective treatment of a pre-existing condition that did not worsen from baseline is not considered an AE.

#### Results in persistent disability/incapacity

The term disability means a substantial disruption of a person's ability to conduct normal life functions.

This definition is not intended to include experiences of relatively minor medical significance such as uncomplicated headache, nausea, vomiting, diarrhoea, influenza, and accidental trauma (e.g., sprained ankle) which may interfere with or prevent everyday life functions but do not constitute a substantial disruption.

#### Is a congenital anomaly/birth defect

#### Other situations:

Medical or scientific judgment should be exercised in deciding whether SAE reporting is appropriate in other situations such as important medical events that may not be immediately life-threatening or result in death or hospitalisation but may jeopardise the participant or may require medical or surgical intervention to prevent one of the other outcomes listed in the above definition. These events should usually be considered serious.

Examples of such events include invasive or malignant cancers, intensive treatment in an emergency room or at home for allergic bronchospasm, blood dyscrasias or convulsions that do not result in hospitalisation, or development of drug dependency or drug abuse.

# 9.3.3. Recording and Follow-Up of AEs and SAEs

#### **SAE Recording**

- When an AE/SAE occurs, it is the responsibility of the investigator to review all
  documentation (e.g., hospital progress notes, laboratory, and diagnostics reports)
  related to the event.
- The investigator will then record all relevant information on AE/SAEs in the eCRF.
- It is **not** acceptable for the investigator to send photocopies of the participant's medical records to GSK in lieu of completion of the GSK AE/SAE eCRF page.
- There may be instances when copies of medical records for certain cases are requested by GSK. In this case, all participant identifiers, with the exception of the participant number, will be redacted on the copies of the medical records before submission to GSK.
- The investigator will attempt to establish a diagnosis of the event based on signs, symptoms, and/or other clinical information. Whenever possible, the diagnosis (not the individual signs/symptoms) will be documented as the AE/SAE.

